
 1. Any condition that, in the opinion of the Investigator or a hepatologist or radiologist, would make liver biopsy contraindicated. This includes (but is not limited to): abnormalities detected on liver ultrasound performed within 28 days of procedure or prior liver ultrasound result within 90 days that would preclude safe performance of the biopsy. 		

NAME OF COMPANY	SUMMARY TABLE	FOR NATIONAL AUTHORITY USE ONLY:
BioMarin Pharmaceutical Inc. [name]	Referring to Part of the Dossier: Volume:	
NAME OF FINISHED PRODUCT: BMN 270	Page:	
NAME OF ACTIVE INGREDIENT: AAV5-hFVIII-SQ	Reference:	
INVESTIGATIONAL PRODUCT(S), DOSE, ROUTE AND REGIMEN: Each subject will receive a single intravenous infusion of BMN 270 at 6E13 vg/kg. The volume of infusion will depend on the subject's weight		
REFERENCE THERAPY(IES), DOSE, ROUTE AND REGIMEN: No reference therapy will be evaluated in this study.		
DURATION OF TREATMENT: BMN 270 is given as a single dose by intravenous infusion.		
CRITERIA FOR EVALUATION: Efficacy: Primary efficacy endpoint: 
 Change of the hFVIII activity, as measured by chromogenic substrate assay, during Weeks 49-52 post-BMN 270 infusion from baseline. Each subject's hFVIII activity during Weeks 49-52 is defined as the median of the values obtained during this 4-week window. Values for hFVIII activity will be excluded if obtained within 72 hours since the last infusion of exogenous FVIII protein concentrates. Secondary efficacy endpoints: 
 Change from baseline in the annualized utilization (IU/kg/year) and infusion rate (number/year) of exogenous FVIII replacement therapy during Week 5 to Week 52 post-BMN 270 infusion, for subjects receiving FVIII prophylaxis during the 12 months prior to study entry or change from baseline in the annualized utilization (mg/kg/year) of emicizumab during Week 27 to Week 52 post-BMN 270 infusion for subjects receiving prior emicizumab prophylaxis. Change from baseline in the annualized number of bleeding episodes requiring exogenous FVIII replacement treatment (annualized bleeding rate, ABR) during Week 5 to Week 52 post-BMN 270 infusion for subjects receiving prior FVIII prophylaxis, or Week 27 to Week 52 post-BMN 270 infusion for subjects receiving prior emicizumab prophylaxis Change from baseline in the total score of Haemo-QoL-A at Week 52 post-BMN 270 infusion 		

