
 • Change from baseline in the annualized utilization (IU/kg/year) of exogenous FVIII replacement therapy during Weeks 5-52 post-BMN 270 infusion, for subjects receiving FVIII prophylaxis during the 12 months prior to study entry, or change from baseline in the annualized utilization (mg/kg/year) of emicizumab during Week 27 to Week 52 post-BMN 270 infusion for subjects receiving prior emicizumab prophylaxis • Change from baseline in the annualized infusion rate (number/year) of exogenous FVIII replacement therapy during Weeks 5-52 post-BMN 270 infusion, for subjects receiving FVIII prophylaxis during the 12 months prior to study entry, or change from baseline in the annualized utilization (mg/kg/year) of emicizumab during Week 27 to Week 52 post-BMN 270 infusion for subjects receiving prior emicizumab prophylaxis • Change from baseline in the annualized number of bleeding episodes (number/year) requiring exogenous FVIII replacement treatment during Weeks 5-52 post-BMN 270 infusion for subjects receiving prior FVIII prophylaxis, or Weeks 27-52 post-BMN 270 infusion for subjects receiving prior emicizumab prophylaxis from baseline 		

Mean change from baseline and associated 95% confidence interval will be calculated for the total score of Haemo-QoL-A at Week 52 post-BMN 270 infusion as well.
		

The incidence of AEs will be summarized by system organ class, preferred term, relationship to study drug, seriousness, and severity. Clinical laboratory test values, vital signs, vector shedding and immune response parameters will be summarized descriptively by visit.
		

The final analysis for the study will be performed after all subjects have been followed for 52 weeks post-BMN 270 infusion (or have discontinued study participation prior to Week 52). No formal interim analysis is planned. Informal analyses (ie, no hypothesis testing) may be performed at different timepoints to assess efficacy and safety over time. The primary efficacy endpoint for such analyses involves hFVIII activity, as measured by chromogenic substrate assay, and is defined as median FVIII activity during a specific 4-week time interval post-BMN 270 infusion.
		

Details of the planned analyses will be specified in the SAP.
		

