8 STUDY OBJECTIVES

The primary efficacy objective of the study is to:

- Assess the efficacy of BMN 270 with prophylactic corticosteroids defined as FVIII activity, as measured by chromogenic substrate assay, during Weeks 49-52 following intravenous infusion of BMN 270

The secondary efficacy objectives of the study are to:

- Assess the impact of BMN 270 with prophylactic corticosteroids on the use of exogenous FVIII replacement therapy from Week 5 to Week 52 for subjects receiving prior FVIII prophylaxis or on use of emicizumab from Week 27 to Week 52 for subjects receiving prior emicizumab prophylaxis
- Assess the impact of BMN 270 with prophylactic corticosteroids on the number of bleeding episodes requiring exogenous FVIII replacement therapy from Week 5 to Week 52 for subjects receiving prior FVIII prophylaxis or on use of emicizumab from Week 27 to Week 52 for subjects receiving prior emicizumab prophylaxis
- Assess the impact of BMN 270 with prophylactic corticosteroids on quality of life as measured by the Haemo-QoL-A questionnaire at Week 52 of the study compared to baseline

The tertiary efficacy objective of the study is to:

- Assess the impact of BMN 270 with prophylactic corticosteroids on patient-reported outcomes (PROs) (other than Haemo-QoL-A) at Week 52 of the study compared to baseline

The exploratory efficacy objective of the study is to:

- Assess the efficacy of BMN 270 with prophylactic corticosteroids defined as FVIII activity, as measured by chromogenic substrate assay, during Weeks 49-52, following intravenous infusion of BMN 270 for subjects with detectable AAV5 total antibodies below the minimum required dilution at Screening

The safety objectives of the study are to:

- Evaluate the safety of BMN 270 with prophylactic corticosteroids during the first 52 weeks following intravenous infusion
- Assess the long-term safety of BMN 270 with prophylactic corticosteroids

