9.1 Overall Study Design and Plan

This is a Phase 3b, single arm, open-label study in hemophilia A patients with residual FVIII levels ≤ 1 IU/dL. Subjects will be enrolled at approximately 10 sites worldwide. Subjects must have high-quality, well-documented historical data available concerning previous bleeding episodes and exogenous FVIII usage over the previous 12 months in order to be eligible to enroll in the study.

Approximately 20 adult subjects with severe HA will receive a 6E13 vg/kg dose of BMN 270 as a single intravenous infusion in conjunction with receipt of a 19-week prophylactic corticosteroid regimen starting on the day of the BMN 270 infusion.

Post-infusion, subjects will be eligible to receive on-demand corticosteroids, as indicated. (Figure 9.1.1).

Figure 9.1.1: 270-303 Study Schema

In order to minimize bias in the ongoing study and to assure safe and ethical conduct of the clinical trial, an independent Data Monitoring Committee (DMC), consisting of experts in clinical trials, statistics, and hemophilia, will be convened. The DMC will have access during the trial to amalgamated FVIII activity levels, FVIII usage, and bleeding data and review available safety and efficacy (eg, FVIII activity) data during the study on an ongoing basis; they may determine, based on emerging data and the risk/benefit profile, that further enrollment should be paused to enable modification of the protocol or discontinued.

The final analysis for the study will be performed after all subjects have been followed for 52 weeks post-BMN 270 infusion (or have discontinued study participation prior to Week 52). After the final analysis, safety and efficacy will then continue to be assessed long-term for a total of approximately 5 years for each subject.

To avoid breakthrough bleeding, subjects will only discontinue exogenous prophylactic FVIII replacement therapy 4 weeks following infusion of BMN 270 or if FVIII activity has consistently increased above 5 IU/dL, whichever is earlier. Four weeks represents the time by which endogenous production of FVIII following gene transfer is expected to be efficacious, based on prior study results. Subjects previously receiving emicizumab, given its approximate 1-month half-life, will remain on emicizumab prophylaxis until BMN 270 infusion, with their final dose administered prior to Day 1.

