9.4.8.1 Concomitant Hemophilia Treatments

To avoid breakthrough bleeding, subjects will only discontinue exogenous prophylactic FVIII replacement therapy 4 weeks following infusion of BMN 270 or if FVIII activity has consistently increased above 5 IU/dL, whichever is earlier. Subjects previously receiving emicizumab, given its approximate 1-month half-life, will remain on emicizumab prophylaxis until BMN 270 infusion, with their final dose administered prior to Day 1.

FVIII replacement therapy can always be taken as needed by the subject for treatment of an acute bleeding episode; the subject must carefully record his treatment and bleeding episodes in his diary. Prophylactic FVIII use can be used on a case-by-case basis and in consultation with the Medical Monitor to prevent bleeding in extenuating circumstances (eg peri-operative).

In addition, information on FVIII usage and bleeding episodes by medical history must be well-documented and available and will be collected from subjects for the 12-month period immediately preceding study enrollment. Further information on the details that should be provided as part of the subject's well-documented medical and FVIII usage history are provided in the Investigator Site File Binder.

In order to enable rigorous comparisons of pre-study versus on-study FVIII usage and bleeding episodes, the Medical Monitor will review each screened patient's prior bleed and hemophilia medication logs to determine if they are of "high-quality". Elements that will be

assessed to judge the quality of such historical data may include, but are not limited to, the following:

- Date, type (eg, joint, muscle, other), location of bleeds
- Date, name, dose (calculated in IU/kg), and reason for use (eg, usual prophylaxis, one-time prophylaxis, treatment for bleed, surgery) of hemophilia medications.

9.4.8.2 Therapeutic Corticosteroid Treatment and/or Alternative Immunosuppressive Agent Treatment of Elevated Hepatic Transaminases

Prior to dosing, all subjects must be screened per steroid prescription guidelines to ensure the subject is eligible to receive corticosteroid treatment as outlined in the protocol. Refer to corticosteroid prescription guidelines for recommended monitoring for, and management of, potential side effects of corticosteroids, including guidance on medications that should be avoided during corticosteroid treatment.

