9.7.3 Secondary Efficacy Variables

9.7.3.1 Factor VIII Replacement Therapy/Bleeding Episodes

Secondary efficacy variables include:

- Change in the annualized utilization (IU/kg/year) and infusion (number/year) rates of exogenous FVIII replacement therapy during Week 5 to Week 52 post-BMN 270 infusion from the baseline number and utilization of exogenous FVIII replacement therapy, for subjects receiving FVIII prophylaxis during the 12 months prior to study entry, or change in administration of exogenous FVIII replacement therapy Week 27 to Week 52 post-BMN 270 infusion for subjects receiving prior emicizumab prophylaxis.
- Change in the annualized number of bleeding episodes requiring exogenous FVIII replacement treatment (annualized bleeding rate, ABR) during Week 5 to Week 52 post-BMN 270 infusion for subjects receiving prior FVIII prophylaxis, or Week 27 to Week 52 post-BMN 270 infusion for subjects receiving prior emicizumab prophylaxis, from the baseline ABR during the 12 months prior to study entry.

Subjects must have high quality documented historical data available concerning previous bleeding episodes and hemophilia treatment over the previous 12 months in order to be eligible to enroll in the study. During the study, subjects will be asked at each study visit to

report the use of factor replacement therapy and the number of bleeding episodes since the previous visit. This information will be captured on the subject's diary or other subject records.

Subjects are strongly encouraged to immediately consult Investigator for guidance regarding exogenous FVIII administration for suspected bleeds or bleeding episodes within the first 30 days post-BMN 270 infusion.

In subjects who experience recurrent bleeding episodes, the Investigator and Medical Monitor will discuss whether to resume prior FVIII prophylaxis or use of emicizumab.

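### For subjects coming from emicizumab, the synopsis defines the therapy-use secondary endpoint as emicizumab use and Section 9.7.3.1 as FVIII use; the synopsis version leaves out how much FVIII they take

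*Protocol*

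**What the plan says.** **Synopsis, Amendment 1.** The first secondary endpoint has two branches. Subjects with prior FVIII prophylaxis are measured on FVIII use (IU/kg/year and infusions/year) over Weeks 5-52. Subjects with prior emicizumab are measured on change in "annualized utilization (mg/kg/year) of emicizumab during Week 27 to Week 52 post-BMN 270 infusion for subjects receiving prior emicizumab prophylaxis". The synopsis analysis text then splits the endpoint into a utilization bullet and an infusion-rate bullet. The second opens with "Change from baseline in the annualized infusion rate (number/year) of exogenous FVIII replacement therapy during Weeks 5-52 post-BMN 270 infusion", yet its emicizumab branch is again mg/kg/year of emicizumab. Section 14.3 of the original protocol reads the same way.

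**Section 9.7.3.1, Amendment 1.** For the same subjects and weeks the variable is "change in administration of exogenous FVIII replacement therapy Week 27 to Week 52 post-BMN 270 infusion for subjects receiving prior emicizumab prophylaxis". No unit is attached to this branch.

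**Treatment rules.** Section 9.1 keeps these subjects on emicizumab until the BMN 270 infusion, "with their final dose administered prior to Day 1". Under Section 9.4.8.1, "FVIII replacement therapy can always be taken as needed by the subject for treatment of an acute bleeding episode". After recurrent bleeding, Section 9.7.3.1 says the investigator and Medical Monitor "will discuss whether to resume prior FVIII prophylaxis or use of emicizumab".

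**Section 8.** The second secondary objective concerns bleeding episodes, but for the emicizumab group it ends in the words of the first objective: "receiving prior FVIII prophylaxis or on use of emicizumab from Week 27 to Week 52". The matching endpoint in the synopsis and in Section 9.7.3.1 is the annualized bleeding rate (ABR) in both groups.

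**The concern.** The protocol fixes one named secondary endpoint twice, with a different drug each time. This is not detail left to the SAP: an SAP author must depart from one section to follow the other.

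The synopsis version is also weak as a measure of benefit. It tracks a drug that the protocol stops for everyone in this group before dosing, and it does not track the amount of the drug they may take instead. A subject who leaves emicizumab and then needs regular FVIII would appear in it as a complete reduction.

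The study has one open-label arm, and each subject's history is the only comparator for therapy use. If the conflict stays open, the choice between definitions can be made after the data have been seen.

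**Working it through.** The protocol states no figure for this endpoint, so there is none to reproduce. The check is a comparison of the two definitions, followed by simple arithmetic.

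**Notation for one prior-emicizumab subject**
- E: baseline emicizumab use (mg/kg/year), above zero.
- F0: baseline FVIII use. The synopsis rationale says emicizumab patients still need on-demand FVIII for breakthrough bleeds, so F0 can be above zero.
- F1: annualized FVIII use in Weeks 27-52.

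**The two changes**
- Synopsis: on-study emicizumab minus E. With no resumption this is 0 − E, or −100% of baseline, whatever F1 is.
- Section 9.7.3.1: F1 − F0.

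| Course in Weeks 27-52 | Synopsis | Section 9.7.3.1 |
|---|---|---|
| No emicizumab, FVIII use falls (F1 < F0) | −100% | negative |
| No emicizumab, FVIII use unchanged | −100% | zero |
| No emicizumab, FVIII use rises (F1 > F0) | −100% | positive |
| Emicizumab resumed at the prior rate for the whole window | about 0% | F1 − F0 |

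In the first three rows the synopsis measure cannot tell the courses apart. The signs are opposite only in the third.

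**How much FVIII can go uncounted.** Weeks 27-52 span 52 − 27 + 1 = 26 weeks, or 182 days. The synopsis rationale gives FVIII prophylaxis as 2-3 times per week. For a subject on that schedule throughout the window:
- 2 × 26 = 52 infusions; 52 × 365.25 / 182 = 104 per year
- 3 × 26 = 78 infusions; 78 × 365.25 / 182 = 157 per year

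None of these enter the synopsis endpoint, and its infusion-rate bullet has no FVIII count for this group. Under Section 9.7.3.1 they would all count. The change in infusion rate would be positive for any baseline below 104 per year. The schedule illustrates the upper end; the protocol does not predict how many subjects would follow it.

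**The window is not the problem.** With the half-life of about 1 month that Section 9.1 gives (taken as 30.4 days), the time from Day 1 to the start of Week 27 is 182 / 30.4 = 5.99 half-lives, and 2^(−5.99) = 1.6% of the drug remains. Starting at Week 27 is reasonable; the conflict is over which quantity is measured.

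**The case against.** It can fairly be said that the synopsis measure mirrors the FVIII branch. There too prophylaxis is stopped by protocol, by Week 4, and the endpoint shows whether the subject returns to the prior therapy. The secondary analyses are descriptive, so no test, alpha or sample size depends on them. All of that stands. The parallel is incomplete, though: the FVIII branch counts the drug used to treat bleeds after dosing, and the emicizumab branch does not.

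A reader might infer more than the documents support:

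- **That FVIII use in this group is never captured.** FVIII-treated bleeds in Weeks 27-52 enter ABR as episodes, and FVIII use is reviewed at visits. What the synopsis omits is the amount and number of infusions, including any given as prophylaxis.
- **That on-study emicizumab is zero by mandate.** Section 9.7.3.1 provides for discussing its use after recurrent bleeding. Zero is the default, not a certainty.
- **That the definitions generally disagree in sign.** Baseline FVIII use can be above zero, so where BMN 270 works both can show a reduction.
- **That prior-FVIII subjects can move to emicizumab uncounted.** This rests on one reading of Section 9.7.3.1. The sentence may mean only that each group resumes its own prior therapy, and Section 9.1 mentions only prior FVIII prophylaxis.
- **That the bleeding analysis is misdirected.** The objective looks like a copying slip, since the ABR endpoint itself is stated correctly for both groups.

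**Conclusion.** The contradiction is real and sits within Amendment 1: synopsis against Section 9.7.3.1, same subjects, same weeks, different drug. The Section 14.3 wording cited is from the original protocol, because the Amendment 1 text available ends at Section 10.2.1; the Amendment 1 synopsis analysis text carries the same content.

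Per affected subject, the synopsis version gives about −100% by default unless emicizumab is resumed. The Section 9.7.3.1 version gives whatever the FVIII record shows, with the opposite sign if FVIII use rises. In the illustrated case, 52-78 infusions go unreported in this endpoint.

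The protocol does not say how many subjects will come from emicizumab. It could be none or many of the approximately 20, so no effect on the group mean can be computed. The primary analysis is unaffected. This is a should-fix.

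**What to change.** Reconcile the synopsis, Section 9.7.3.1 and Section 14.3 to one definition:

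1. For prior-emicizumab subjects, report both emicizumab (mg/kg/year) and exogenous FVIII (IU/kg/year and infusions/year) over Weeks 27-52, each against the 12-month baseline.
2. In the infusion-rate bullet, replace the repeated emicizumab measure with FVIII infusions per year for this group.
3. Summarise by prior-therapy group.
4. State whether Section 9.7.3.1 is meant to allow emicizumab in prior-FVIII subjects. If so, report that use alongside their FVIII use.
5. In the synopsis and Section 8, reword the second secondary objective as bleeding episodes in both groups, to match the ABR endpoint.

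The cost is a wording change and extra tabulation. Inclusion criterion 2 and Table 9.1.1 already require 12 months of hemophilia therapy history, and Tables 9.1.2 and 9.1.3 already schedule review of FVIII use and concomitant medications after infusion. No visit, sample or treatment rule changes.

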14.3 Secondary Efficacy Endpoints

The analyses of the secondary efficacy endpoints will be descriptive. Mean and associated 95% confidence interval will be provided for the following secondary endpoints, where the baseline value will be derived from the data in the approximately 12-month period prior to BMN 270 infusion:

- Change from baseline in the annualized utilization (IU/kg/year) of exogenous FVIII replacement therapy during Weeks 5-52 post-BMN 270 infusion, for subjects receiving FVIII prophylaxis during the 12 months prior to study entry, or change from baseline in the annualized utilization (mg/kg/year) of emicizumab during Week 27 to Week 52 post-BMN 270 infusion for subjects receiving prior emicizumab prophylaxis
- Change from baseline in the annualized infusion rate (number/year) of exogenous FVIII replacement therapy during Weeks 5-52 post-BMN 270 infusion, for subjects receiving FVIII prophylaxis during the 12 months prior to study entry, or change from baseline in the annualized utilization (mg/kg/year) of emicizumab during Week 27 to Week 52 post-BMN 270 infusion for subjects receiving prior emicizumab prophylaxis
- Change from baseline in the annualized number of bleeding episodes (number/year) requiring exogenous FVIII replacement treatment during Weeks 5-52 post-BMN 270 infusion for subjects receiving prior FVIII prophylaxis, or Weeks 27-52 post-BMN 270 infusion for subjects receiving prior emicizumab prophylaxis

Mean change from baseline and associated 95% confidence interval will be calculated for the total score of Haemo-QoL-A at Week 52 post-BMN 270 infusion as well.

The missing value of the change for annualized utilization and annualized infusion rate will be imputed as 0. The missing value of the change for annualized number of bleeding episodes will be imputed using the median value of the changes of all observed cases.

A sensitivity analysis is planned to analyze ABR using a generalized linear mixed model assuming negative binomial as the underlying distribution. The model will include period (pre- to post-BMN 270 infusion) as the only factor, repeated within subject. The actual number of bleeding episodes will be used as the dependent variable with the time period adjustment (annualization) being implemented as the offset.

To assess the impact of missing data, analyses using observed case are planned as sensitivity analyses for the secondary endpoints. Multiple imputation methods may also be performed.

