For the primary efficacy endpoint at Week 52 (ie, the change in the hFVIII activity during Weeks 49-52 post-BMN 270 infusion from baseline, as measured by chromogenic substrate assay), a one-sample t-test will be used to test the null hypothesis that the change is 0 or less against the alternative hypothesis that the change is greater than 0. Baseline value of 1 IU/dL (eligible subjects must have residual FVIII levels \leq 1 IU/dL as evidenced by medical history) will be used in the calculation of change from baseline since all the subjects will be on prophylactic hemophilia therapy prior to BMN 270 infusion where the FVIII activity level cannot be reliably measured. Descriptive summaries of the proportions of subjects whose FVIII activity during Weeks 49-52 is greater than or equal to select thresholds, such as 5, 15, 25, 30, and 40 IU/dL, and the confidence intervals of the proportions will also be provided.		
The analyses of the secondary and tertiary efficacy endpoints will be descriptive. Mean and associated 95% confidence interval will be provided for the following secondary endpoints, where the baseline value will be derived from the data in the approximately 12-month period prior to BMN 270 infusion:		

NAME OF COMPANY	SUMMARY TABLE	FOR NATIONAL AUTHORITY USE ONLY:
BioMarin Pharmaceutical Inc. [name]	Referring to Part of the Dossier:	
NAME OF FINISHED PRODUCT: BMN 270	Volume:	
NAME OF ACTIVE INGREDIENT: AAV5-hFVIII-SQ	Page: Reference:	

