Subjects receiving 6E13 vg/kg in 270-201 received a different corticosteroid regimen than subjects in 270-301; in 270-201, subjects were started on corticosteroids by Week 3 (either therapeutically, in response to an alanine aminotransferase [ALT] elevation, or prophylactically), whereas in 270-301 subjects received corticosteroids only in response to an ALT elevation. Possibly as a result of this difference, subjects receiving 6E13 vg/kg in 270-201 started corticosteroids at an earlier date in reference to the date of BMN 270 infusion, showed later advent of first ALT elevations, and were also less likely to experience a significant decline in FVIII activity concurrently with an ALT elevation when compared with subjects in 270-301 (20% of subjects in 270-201 vs. 58% of subjects in 270-301). In 270-301, ALT elevation within the first 26 weeks was associated with decreased FVIII activity. Recently published data from 270-201 suggests that corticosteroids may have assisted in rescue or protection of FVIII levels during elevations of ALT and in resolution of elevated ALT levels in some subjects (Pasi, 2020).

The current study is a Phase 3b, single arm, open-label study designed to assess whether BMN 270, at a dose of 6E13 vg/kg with prophylactic corticosteroids, can safely and effectively improve the FVIII activity profiles and alter the clinical phenotype of hemophilia A patients with residual FVIII activity \leq 1 IU/dL.

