7.3.1 Optional Liver Biopsy Rationale

The usual pattern of response in hFVIII activity observed so far after administration of BMN 270 demonstrates peak expression levels during the first 6-12 months post-treatment followed by a decline to a steady-state level of expression thereafter. One of the explanations may lie in the kinetics of vector genome processing, which involves a series of steps such as DNA degradation and repair, annealing, and circularization that can result in the formation of stable, double-stranded, circularized transgene DNA forms. It is these circularized DNA species that are thought to be associated with long-term, persistent expression of the gene product in target cells. Examination of transduced hepatocytes from subjects treated with BMN 270 in the 270-303 study will help to establish whether DNA circularization may occur and could account for the long-term hFVIII expression observed in humans.

Additionally, health of the liver after gene transduction has been monitored indirectly by periodic assessments of hepatic enzymes released into the blood stream. Transient, post-treatment elevations in ALT levels have been observed in the majority of subjects, as well as inter-subject variability in post-therapy FVIII activity levels. Neither the reasons for nor the significance of the ALT elevations or the variations in response to FVIII gene therapy are known. Moreover, the effects of BMN 270 on hepatic tissue structure and function are also currently unknown. Finally, a call to incorporate liver biopsy sub-studies into gene therapy trials for hemophilia has been issued by medical and scientific leaders in the field to help illuminate these and other questions ([National Hemophilia Foundation, 2019](#)).

The purpose of this exploratory sub-study is to provide a better understanding of the long-term gene expression related to genome circularization, health of the liver, and variation in FVIII activity levels observed after gene therapy with BMN 270. With use of prophylactic corticosteroids, it is believed that there will be stable hepatic function and FVIII activity expression, with tolerance of prophylactic corticosteroid therapy and no change to the risk of thromboembolism. This sub-study aims to evaluate the effect on the liver by performing liver biopsies at approximately Week 26, Week 52, and/or during Years 2-5.

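### The bleeding-rate change mixes two post-infusion windows and two baseline therapies, and the protocol provides no split by prior prophylaxis

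*Protocol*

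**What the plan says.** The Amendment 1 synopsis (Statistical Methods, Analysis) defines one ABR endpoint with two counting periods: "Weeks 5-52 post-BMN 270 infusion for subjects receiving prior FVIII prophylaxis, or Weeks 27-52 post-BMN 270 infusion for subjects receiving prior emicizumab prophylaxis". The secondary endpoints in the same synopsis and Section 9.7.3.1 give the same windows. Baseline is drawn from roughly the 12 months before infusion, when each subject was on his own prophylaxis.

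On the summary, the synopsis states: "Mean and associated 95% confidence interval will be provided for the following secondary endpoints". It names no split by prior prophylaxis. It also states: "The analyses of the secondary and tertiary efficacy endpoints will be descriptive".

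Section 14.3 of the original protocol adds a negative binomial sensitivity model for ABR, with follow-up time as offset: "The model will include period (pre- to post-BMN 270 infusion) as the only factor, repeated within subject". A missing change in the number of bleeds "will be imputed using the median value of the changes of all observed cases". The Amendment 1 counterpart of Section 14.3 is not in the text available, but the amendment's summary of changes lists no statistical change.

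Three further statements bear on the point. The study rationale in the synopsis says that emicizumab has given lower bleed rates than earlier FVIII prophylaxis. Inclusion criterion 2 accepts any prophylactic hemophilia therapy, and no cap on the prior-emicizumab share was found. Section 7.3.1 describes "peak expression levels during the first 6-12 months post-treatment followed by a decline to a steady-state level of expression thereafter".

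**The concern.** Annualizing, or using an offset, corrects for how long a subject is followed. It does not correct for which weeks are counted or for what the baseline represents. Here both differ by prior prophylaxis:

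- Weeks 5-26 count for prior-FVIII subjects and never for prior-emicizumab subjects. Those weeks hold most of the suggested 19-week corticosteroid course. They also fall in the period in which, in 270-301, "ALT elevation within the first 26 weeks was associated with decreased FVIII activity" (Section 7.3).
- The change is measured against FVIII prophylaxis in one group and against emicizumab in the other.

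If the groups are averaged, the result is a blend of two different contrasts, weighted by whatever case mix happens to enroll. Two trials with the same effect in every subject could report different mean changes. The imputation rule carries the problem further, because a missing change in one group is filled from a median to which the other group contributes, possibly as the majority.

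**Working it through.** The protocol states no size, power or expected value for the bleeding rate, so there is no figure of its own to reproduce on this point.

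**Windows (from the endpoint definition)**
- Prior FVIII: 52 − 5 + 1 = 48 weeks. One bleed annualizes to 365.25/(7 × 48) = 1.09 per year.
- Prior emicizumab: 52 − 27 + 1 = 26 weeks. One bleed annualizes to 365.25/(7 × 26) = 2.01 per year.
- Weeks 5-26 are 22 weeks: 22/48 = 46% of the first window and none of the second. Weeks 27-52 are 26/48 = 54% of the first window.

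**Formula**
Let both groups bleed at rate *e* in Weeks 5-26 and *l* in Weeks 27-52, with baselines *bF* (FVIII) and *bE* (emicizumab), and let *s* be the prior-emicizumab share.
- Change, prior FVIII: *cF* = (22*e* + 26*l*)/48 − *bF*
- Change, prior emicizumab: *cE* = *l* − *bE*
- Window part: *W* = (22/48)(*e* − *l*)
- Pooled change: (1 − *s*)*cF* + *s* *cE* = *cF* + *s*[(*bF* − *bE*) − *W*]

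The sign of the bracket decides the direction. If the baseline gap exceeds *W*, more emicizumab subjects make the reduction look smaller; if *W* exceeds the gap, they make it look larger.

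**Size of the window part (rates assumed; the documents give no post-infusion rates)**
- Equal rates: 0
- 1.0 versus 0.5: 22/48 × 0.5 = 0.23 per year
- 2.0 versus 0.5: 22/48 × 1.5 = 0.69 per year

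**Pooled change.** The baseline of 4 is the upper end of the median range of 1-4 that the synopsis cites for FVIII prophylaxis. The emicizumab baseline is assumed, because the protocol says only that it is lower.

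| *bF* / *bE* | *e* / *l* | As written, *s* = 0 / 25 / 50% | Common Weeks 27-52, *s* = 0 / 25 / 50% |
|---|---|---|---|
| 4 / 4 | 1.0 / 1.0 | −3.00 / −3.00 / −3.00 | −3.00 / −3.00 / −3.00 |
| 4 / 4 | 2.0 / 0.5 | −2.81 / −2.98 / −3.16 | −3.50 / −3.50 / −3.50 |
| 4 / 1 | 1.0 / 1.0 | −3.00 / −2.25 / −1.50 | −3.00 / −2.25 / −1.50 |
| 4 / 1 | 2.0 / 0.5 | −2.81 / −2.23 / −1.66 | −3.50 / −2.75 / −2.00 |

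Worked for the last row: *cF* = (22 × 2.0 + 26 × 0.5)/48 − 4 = 1.19 − 4 = −2.81; *cE* = 0.5 − 1 = −0.50; at 50% the mean of the two is −1.66.

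Row 2 shows the window effect alone and row 3 the baseline effect alone; they run in opposite directions. In rows 3 and 4 the common window leaves the dependence on case mix in place.

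**Imputation.** In the last row the two groups' changes are 2.81 − 0.50 = 2.31 bleeds per year apart. That is the scale of error when a missing value in one group is filled from a median dominated by the other.

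**Reason for the later start.** The protocol gives emicizumab a half-life of about one month, with the last dose before Day 1. With a half-life of 28 to 30.4 days and the last dose at about Day 1, 0.5^(28/half-life) = 50-53% remains at the start of Week 5 and 0.5^(182/half-life) = 1.1-1.6% at the start of Week 27.

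**The case against.** **Pooling is never stated.** The endpoint bullets join the two populations with the word or. In the utilization bullets the same construction joins IU/kg and mg/kg, which cannot be averaged, so group-specific reporting may be intended for ABR too, and the display could be left to the SAP. This stands in part: pooling of the mean is implied, not written. But ABR has the same unit in both groups, so nothing prevents averaging, and the model and the imputation rule in Section 14.3 do combine the groups.

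**The Section 14.3 wording is from the original protocol.** True. Its survival into Amendment 1 is an inference from the summary of changes, and the model is only a sensitivity analysis.

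**The later start is justified.** This stands. Counting prior-emicizumab subjects from Week 5 would credit BMN 270 with protection while about half the emicizumab remained. The protocol does not itself link this to Week 27, but the reason is evident, and the windows should stay.

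**A reader might infer that prior-emicizumab subjects are scored only at peak expression, so that the pooled result flatters the product as their share rises.** The documents do not support that. The phrase "peak expression levels during the first 6-12 months post-treatment" can mean months 6 to 12, which Weeks 27-52 match, or any time within the first 6 to 12 months; the prior-FVIII window also covers Weeks 27-52. No post-infusion bleed rates are given, the overall study plan expects efficacy by four weeks, and the link between ALT and FVIII in the first 26 weeks comes without a bleed rate. The endpoint is a change, and a lower emicizumab baseline can reverse the direction.

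**Conclusion.** The concern holds in a limited form. As the protocol stands, any combined ABR change blends a 48-week and a 26-week window and two baseline therapies, in proportions that nothing controls. The window part is (22/48) times the difference between early and late bleed rates: nil if they are equal, and 0.23 to 0.69 per year for the two assumed pairs. The baseline part can be larger and run the other way: with assumed baselines of 4 and 1, the pooled change moves from −2.81 to −1.66 as the emicizumab share goes from 0 to 50%. These sizes assume the same post-infusion rates in both groups. They illustrate how far a pooled figure could move and do not predict it.

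The documents establish neither that bleeding is more frequent in Weeks 5-26 nor a bias in a known direction. Because the analysis is descriptive, no type I error rate and no primary conclusion is at stake; what suffers is the interpretation of a secondary mean and its interval.

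**What to change.** Keep the group-specific windows and change the following:

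- State that the mean change in ABR and its 95% confidence interval are reported separately by prior prophylaxis.
- Fit the negative binomial model within each prior-prophylaxis group, or for prior-FVIII subjects only if the emicizumab group is too small. Fix the minimum group size in advance.
- Impute a missing change from the median of the subject's own prior-prophylaxis group.
- Label any pooled mean as supportive and show the number of subjects from each group beside it.
- State the reason for starting at Week 27.

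A pooled figure on the common Weeks 27-52 window may be added as a sensitivity analysis. It removes the window part but not the baseline difference, and it discards 22 of 48 weeks for prior-FVIII subjects, so it should not replace the separate estimates.

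The cost is a few table columns and a sentence each for the model and the imputation; no new data are needed. With about 20 subjects, each estimate rests on fewer people and has a wider interval, and the emicizumab group may support little more than a listing.
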